8.2 Criteria for Assessing the Severity of Adverse Events

CTCAE Version 5.0 Grading

- Grade 1: Mild; asymptomatic or mild symptoms; only observed clinically or diagnostically; no treatment required
- Grade 2: Moderate; requires minimal, local, or non-invasive treatment; limitation of instrumental activities of daily living appropriate for age
- Grade 3: Severe or medically significant but not immediately life-threatening; hospitalization or prolongation of hospital stay required; disability; limitation of self-care activities of daily living
- Grade 4: Life-threatening; requires urgent treatment
- Grade 5: Death related to the AE

8.3 Criteria for Assessing the Relationship between Adverse Events and the Investigational Medication

Adverse events include all unexpected clinical manifestations that should be reported as AEs, regardless of whether they are related to the trial medication, whether the subject is assigned to the medication group, or even whether the medication is administered. All adverse events must be reported in the form of a clinical report. Any discomfort complained of by the subject during the treatment period, or any abnormal changes in objective laboratory test indicators, should be truthfully recorded, along with the severity, duration, treatment measures, and outcome of the adverse event. The clinical physician should combine medical knowledge, clinical experience, and the safety characteristics of the medication to conduct a comprehensive analysis and judgment of the possible relationship between adverse events and the trial medication, using a five-level classification ofdefinitely related, likely related, possibly related, possibly unrelated, and unrelated. Definitely related, likely related, and possibly related are all classified as adverse drug reactions. When calculating the incidence of adverse reactions, these three categories are combined as the numerator, and the total number of subjects evaluated for safety is used as the denominator.

Table 11 Criteria for Assessing the Relationship between Adverse Events and the Investigational Medication

Causality	Criteria for Assessment	
Related	The occurrence of the adverse event	
	is temporally related to the	
	administration of the medication.	
	The investigational medication is a	
	more plausible explanation for the	
	adverse event than other causes	

	, , , , , , , , , , , , , , , , , , , ,	
	(e.g., the subject's pre-existing	
	conditions, environmental or toxic	
	factors, or other treatments the	
	subject has received).	
	The adverse event resolves or	
	decreases after discontinuation or	
	dose reduction of the medication.	
	It is consistent with known AE types of	
	the suspected drug or its	
	pharmacological class.	
	The adverse event reappears upon	
	re-administration of the medication.	
Possibly Related	The occurrence of the adverse event	
	is temporally related to the	
	administration of the medication.	
	The investigational medication shares	
	equal plausibility with other causes	
	(e.g., the subject's pre-existing	
	conditions, environmental or toxic	
	factors, or other treatments the	
	subject has received) in explaining the	
	adverse event.	
	The adverse event resolves or	
	decreases after discontinuation or	
	dose reduction of the medication, if	
	applicable.	
Unlikely Related	Other causes (e.g., the subject's pre-	
Offinely Netaleu		
	existing conditions, environmental or	
	toxic factors, or other treatments the	
	subject has received) are more	
	plausible explanations for the adverse	
	event than the investigational	
	medication.	
	The adverse event does not resolve or	
	decrease after discontinuation or dose	

	reduction of the medication, if applicable, or the situation is unclear.	
	The adverse event does not reappear	
	upon re-administration of the	
	medication, or the situation is unclear.	
Definitely Unrelated	The occurrence of the adverse event is	
	not temporally related to the	
	administration of the medication, or	
	The adverse event has another obvious	
	cause (e.g., the subject's pre-existing	
	conditions, environmental or toxic	
	factors, or other treatments the subject	
	has received).	
Unable to Determine	The information above is insufficient,	
	and based on the available information,	
	the investigator believes it is impossible	
	to determine, and the investigator	
	cannot obtain further follow-up	
	information.	

8.4 Serious Adverse Events (SAEs)

Serious adverse events are medical events that occur during the clinical trial process and require hospitalization or prolongation of hospital stay, disability, affect the ability to work, are life-threatening, or result in death, congenital malformations, etc. These include the following unexpected medical events:

- Events that result in death;
- Life-threatening events (defined as events where the subject is at risk of death at the time of occurrence);
- Events that require hospitalization or prolongation of hospital stay;
- Events that result in permanent or significant disability/incapacity/affecting the ability to work;
- Congenital anomalies or birth defects.

8.4.1 Pregnancy

Pregnancies occurring during the clinical trial should be reported as serious adverse events, along with a specializedPregnancy Report Form.

8.4.2 Disease Progression

Disease progression (including symptoms and signs of progression) should not be reported as serious adverse events. However, if death occurs due to disease progression within the trial or safety reporting period, it should be reported as a serious adverse event. Hospitalization due to symptoms and signs of disease progression should not be reported as a serious adverse event. If the final outcome of cancer is death within the trial or safety reporting period, the event leading to death must be reported as a serious adverse event. 8.4.3 Undertaking Other Anticancer Treatments

Recording of adverse events begins from the start of medication administration until 30 days after discontinuation. If subjects start other anticancer treatments after 30 days, there is no need to continue recording and tracking non-fatal adverse events. If death occurs within the serious adverse event reporting period after the end of study treatment, it must be reported regardless of whether the patient has received other treatments.

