- 12. Tumor assessment includes RECIST 1.1 assessment. It is assessed by the investigator and must include the cervical, thoracic, abdominal, and pelvic regions. According to the RECIST v1.1 criteria, baseline (within 28 days before the first dosing), an assessment is conducted every 6 weeks (±7 days); after 24 weeks of medication, an assessment can be done every 9 weeks (±7 days) until disease progression, initiation of new antitumor treatment, withdrawal of ICF by the subject, or death. Subjects who experience disease progression for the first time, if their clinical condition is stable, the investigator will determine whether they can continue treatment.
- 13. Subjects are required to provide archived or fresh tumor tissue samples during the screening phase.
- 14. Subjects are required to provide a 10 ml whole blood sample for the detection of tumor biological markers at the following time points: before the first dosing, during the treatment phase before the next treatment and imaging assessment, and when disease progression is confirmed.
- 15. Safety follow-up will be conducted 30±3 days after the last dosing or before the initiation of new antitumor treatment, whichever occurs first. All AEs occurring before the safety follow-up visit should be recorded until they are resolved to grade 0-1 or baseline levels, or the investigator deems further follow-up is unnecessary for justified reasons (whichever occurs first). SAEs occurring within 90 days after the last dosing or before the subject starts new anticancer treatment (whichever occurs first) should be followed up and recorded.

16. Survival follow-up: Conducted every 90 days (±7 days) after the safety visit, which can be done via telephone.						

Contents

1 RE	ESEARCH BACKGROUND	18
	1.1 DISEASE BACKGROUND	18
	1.2 RISK AND BENEFIT ASSESSMENT	22
2 RE	ESEARCH PURPOSE	22
	2.1 Main Purpose	22
	2.2 Secondary Purposes	22
	2.3 EXPLORATORY PURPOSES	22
3 ST	TUDY DESIGN	22
	3.1 Overall Design	22
	3.1.1 Sample Size Estimation	23
4 ST	FUDY POPULATION	23
	4.1 Inclusion Criteria	23
	4.2 Exclusion Criteria	25
	4.3 RESTRICTIONS DURING THE STUDY PERIOD	26
	4.3.1 Pregnancy	26
	4.3.2 Fertility	26
	4.3.3 Lactation	27
	4.4 CRITERIA FOR SUBJECT DISCONTINUATION OF TREATMENT/WITHDRAWAL FROM TH	E STUDY
•••		
	4.4.1 Discontinuation of Study Treatment	28
	4.4.2 Withdrawal from the Study	28
	4.4.3 Clinical Criteria for Early Termination of the Study	29
5 ST	TUDY MEDICATION AND OTHER TREATMENTS	29

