6.2.5 Subsequent Anticancer Treatment Status

All new anticancer treatments initiated after the last drug administration should be reviewed by the investigator or a qualified designated personnel. If a subject starts a new anticancer treatment within 30 days after the last administration of the trial treatment, a safety follow-up visit must be conducted before the first administration of the new treatment.

After starting a new anticancer treatment, the subject will enter the survival follow-up. For detailed instructions on survival status follow-up, please refer to Section 6.2.4 - Survival

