Disease progression is defined as a deterioration in the subject's condition caused by the primary tumor targeted by the investigational medication, with the appearance of new lesions related to the primary tumor or the progression of existing lesions considered as disease progression. Expected disease progression is not reported as an AE. Deaths, life-threatening conditions, hospitalizations or prolongation of hospital stays, permanent or severe disabilities/loss of abilities, congenital abnormalities/birth defects, and other significant medical events caused by expected disease progression symptoms and signs are not accelerated as serious adverse events (SAEs) for reporting.

New Anticancer Treatments

Within 90 days after the last administration, if a subject begins new anticancer treatments, only serious adverse events considered related to the study medication are recorded and reported.

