8.7.1 Immune-Related Adverse Events

Given the mechanism of action of Sintilimab, which induces T-cell activation and proliferation, immune-related adverse events (irAEs) may be observed during this study. Signs and symptoms of irAEs in subjects should be monitored. If there is no clear alternative etiology (e.g., infection), signs or symptoms of diseases occurring during the trial in subjects should be considered related to the immune system.

Dose adjustments for Sintilimab and principles for adverse event management are detailed in Sections 5.2 and 5.3 of the protocol.

9 Statistical Analysis

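### The protocol gives conflicting recording windows for non-serious adverse events, and on the likelier reading new non-serious immune-related events after about day 30 are not recorded

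*Protocol*

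**What the plan says.** **Start of recording.** Section 8.1 counts AEs from the signing of consent, and Table 1 ticks AE assessment at screening. Section 8.4.3 starts at first dose: "Recording of adverse events begins from the start of medication administration until 30 days after discontinuation".

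**End of recording.**
- Sections 8.4.3 and 3.1 use 30 days after treatment.
- The second sentence of 8.4.3 says that non-fatal AEs need no further recording or tracking once other anticancer therapy begins after day 30.
- Table 1 note 15 ties recording to the safety visit: "All AEs occurring before the safety follow-up visit should be recorded until they are resolved to grade 0-1 or baseline levels". Section 6.2.3 says the same. The visit can move: "Safety follow-up will be conducted 30±3 days after the last dosing or before the initiation of new antitumor treatment, whichever occurs first".
- Table 1 ticks AE assessment in all seven columns, including survival follow-up. Section 7.2 has AEs assessed in follow-up as the flowchart requires. Note 10, attached to that row, refers recording and reporting timelines to Section 8, and 7.2 also refers recording to Section 8.
- Section 6.2.4 lists survival, later therapy and progression for survival contacts, with no AE item. Note 16 gives the timing: "Conducted every 90 days (±7 days) after the safety visit, which can be done via telephone".

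**After new therapy.** Section 6.2.5: "After starting a new anticancer treatment, the subject will enter the survival follow-up". Within 90 days of the last dose, 8.4.5 then limits collection: "only serious adverse events considered related to the study medication are recorded and reported".

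**Immune-related events.** Section 5.3 warns that irAEs may begin months after dosing ends. Section 8.7.1 sets no end date: "Signs and symptoms of irAEs in subjects should be monitored". The Evaluation Criteria in the Protocol Summary list irAE incidence and severity.

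**The concern.** A site that wants to know when to stop recording a new non-serious AE finds several answers. Two consequences follow.

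First, the protocol names late irAEs as a risk, makes irAE incidence a safety measure, and asks for irAE monitoring without an end date. Yet its most likely recording rule stops at about day 30. An incidence to day 30 is correct for that window, but it cannot show non-serious irAEs that begin later. An analysis plan cannot repair this afterwards, because the events will not have been collected.

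Second, where rules differ, staff may record late events for some patients and not for others. The reported percentage would then belong to no defined window. In a single-arm trial of 45, one patient is 1/45 = 2.2 percentage points if all 45 are in the safety set, so a few patients handled differently would be visible.

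**Working it through.** No sample size, power or event figure is involved, and the protocol states no figure to reproduce. The check sets the rules side by side and then works out the schedule.

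**1. The windows**

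| Source | Start | End for a new non-serious AE |
|---|---|---|
| 8.1, Table 1 screening tick | consent | not stated |
| 8.4.3, first sentence | first dose | day 30 |
| 3.1 | AEs monitored throughout the trial | 30-day safety follow-up |
| Note 15, 6.2.3 | not stated | safety visit: day 27 to 33, or earlier if new therapy starts |
| 8.4.3, second sentence | – | by implication past day 30, until new therapy |
| Table 1 survival tick, with 7.2 | – | survival follow-up |
| 6.2.4 | – | no AE content at survival contacts |

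**2. Which rule governs.** Section 7.2 points to the flowchart for when AEs are assessed and to Section 8 for how they are recorded. Note 10 sends the flowchart row to Section 8. Section 8 is therefore the likelier authority, and its explicit limit is day 30. The survival tick may serve only the note 15 duties: following AEs already begun until they resolve, and collecting serious AEs (SAEs) to day 90 or new therapy.

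**3. Late irAEs under that reading.** A new non-serious irAE with onset after about day 30 has no clear recording rule. Section 7.2 requires an immune-cause check only for unexplained events arising on study treatment, and 8.4.5 narrows collection to related SAEs once new therapy starts.

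**4. New therapy before day 30.** Let it start on day d, with the safety visit held that day. Section 8.4.3 records to day 30. Read as a stopping rule, note 15 ends at day d. The difference is 30 − d days. For assumed d:
- d = 7: 30 − 7 = 23 days
- d = 14: 30 − 14 = 16 days
- d = 21: 30 − 21 = 9 days

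**5. First survival contact.** From notes 15 and 16, (30 ± 3) + (90 ± 7) runs from 27 + 83 = day 110 to 33 + 97 = day 130. The Table 1 grid gives the safety visit ±7 days, hence 23 + 83 = day 106 to 37 + 97 = day 134. Day 110 to 130 is 20 to 40 days after day 90. If the safety visit moves to day d, the contact falls at d + 83 to d + 97; for d = 14 that is day 97 to 111. It can precede day 90 only if d is below 7.

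These are lengths of schedule, not sizes of effect.

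**The case against.** The strongest reply is that there is one nominal window. Sections 3.1 and 8.4.3, note 15 and 6.2.3 all centre on day 30, a legitimate choice for non-serious AEs. That stands, and nothing here argues against 30 days for AEs in general.

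Several stronger readings are tempting, and the protocol does not support them.

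- **That the survival tick has no limit.** Note 10 states no day, but it limits the tick by referring to Section 8.
- **That late non-serious irAEs are certainly lost.** The second sentence of 8.4.3 implies that recording may run past day 30, although it could mean only the tracking of open events. Section 4.4.1 also asks for important clinical event data up to the last scheduled visit. Patients who stop without progression keep attending for imaging and questionnaires, but 7.1.3 and 7.3 attach no AE recording to those visits. The loss depends on which reading a site follows.
- **That note 15 must cut recording off when the visit moves earlier.** It can be read as a duty to follow events already begun, with 8.4.3 still running to day 30. The differences of 23, 16 and 9 days hold only on the stricter reading.
- **That serious toxicity is missed.** An irAE that hospitalises, disables or threatens life is an SAE. Section 8.5 keeps drug-related SAEs reportable after day 90.

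The table was read from a PDF, and neighbouring rows look unreliable: the ECOG row is blank, and the quality-of-life row disagrees with note 11. The AE row has seven marks for seven columns, so misalignment is unlikely, but the tick should be checked in the original. The conflicts between 8.1 and 8.4.3, and between 8.4.3 and 6.2.3, do not depend on it.

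The analysis window for irAE incidence may properly be left to the analysis plan. What is collected cannot be.

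**Conclusion.** The point holds at low severity. The protocol gives two starts and several ends for recording non-serious AEs. On the likelier Section 8 reading, new non-serious irAEs that begin after about day 30 are not recorded, despite the warning in 5.3 and the listing of irAE incidence as a safety measure.

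The undercount cannot be computed, because the protocol gives neither an irAE rate nor a late-onset share. The conclusion assumes that Section 8 governs over the flowchart and that the first sentence of 8.4.3 is the operative limit. Late related SAEs and the primary endpoint, the 1-year PFS rate, are not affected.

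**What to change.** 1. **State one window in 8.4.3**: non-serious AEs are recorded from consent to day 30 after the last dose, whether or not the safety visit is brought forward. Align note 15 and 6.2.3 with it.
2. **Add an irAE rule** to 8.4.3 and 6.2.4, and as a footnote to the Table 1 survival tick: new irAEs of any grade with onset up to day 90 after the last dose are asked about and recorded at the first scheduled survival contact, with the onset date and the start date of any new therapy. If that contact falls before day 90, use the next one. Day 90 matches the SAE limit in note 15 and 8.5. A fixed onset limit gives every patient the same window, which recording up to the contact date would not.
3. **Add a matching exception to the new-therapy rule in 8.4.5**, so that it does not cancel items 1 and 2.
4. **Report irAE incidence to day 30 and to day 90**, with a count that excludes events starting after new therapy.

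The cost is one footnote, short wording changes, a few questions at a contact already scheduled, and an extra table row. The drawbacks are that recall by telephone is less complete and that attribution is less certain after new therapy, which is why the separate count is needed.

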8.4.4 Hospitalization

Adverse events that result in hospitalization or prolongation of hospital stay during clinical research should be considered serious adverse events. Any initial admission to a medical institution (even if less than 24 hours) meets this criterion.

Hospitalization does not include the following situations:

- Rehabilitation institutions
- Convalescent homes
- Routine emergency room admissions
- Same-day surgeries (e.g., outpatient/same-day/non-hospitalized surgeries)

Hospitalization or prolongation of hospital stay not related to the worsening of adverse events (AEs) itself is not a serious adverse event (SAE). For example:

- Hospitalization due to a pre-existing condition without the occurrence of new AEs or exacerbation of the existing condition (e.g., for the examination of laboratory test abnormalities that have persisted since before the trial)
- Hospitalization for administrative reasons (e.g., routine annual medical examinations)
- Hospitalization stipulated in the clinical trial protocol (e.g., operations required by the protocol)
- Elective hospitalization not related to the worsening of AEs (e.g., elective cosmetic surgery)
- Scheduled treatments or surgeries should be recorded in the entire trial protocol and/or the subject's baseline information
- Hospitalization solely due to the use of blood products

Diagnostic or therapeutic invasive (e.g., surgical) and non-invasive procedures should not be reported as AEs. However, if the disease condition that leads to such a procedure which meets the definition of an adverse event, should be reported. For example, acute appendicitis occurring during the AE reporting period should be reported as an AE, and the subsequent appendectomy should be recorded as a treatment method for that AE.

Death should not be reported as the term for serious adverse events. The medical term for the SAE that leads to death (if there is a diagnostic name, the diagnostic name should be used) is the reporting term for serious adverse events, while death is the outcome of the adverse event.

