The primary endpoint of this study is the 1-year PFS rate, defined as the proportion of patients without disease progression at one year.

Sample Size

Based on previous research data, the 1-year PFS rate for patients with extensive-stage SCLC receiving first-line chemotherapy does not

Estimation

exceed 5.4%. It is estimated that the use of first-line Sintilimab combined with chemotherapy can increase the 1-year PFS rate of patients to 15%. Through sample size calculation, with α =0.05 (one-sided test), Power=80%, and assuming a dropout rate of 10%, using the One-Sample Logrank Test, a total of 45 patients are required to be enrolled.

- (1) Age: ≥18 years and ≤75 years old;
- (2) A confirmed diagnosis of extensive-stage small cell lung cancer (SCLC) by pathological examination (including histology or cytology);
- (3) Previously untreated patients who have not received any systemic antitumor therapy;
- (4) Asymptomatic patients with brain metastases, or those with brain metastases that have been treated and maintained a clinically stable condition for at least one month, and have not used corticosteroids and anticonvulsant medications for at least one month prior to entering the study;
- (5) Measurable lesions (as defined by RECIST 1.1, the long diameter of the tumor lesion on CT scan is ≥10mm, the short diameter of the lymph node lesion on CT scan is ≥15mm, the scan slice thickness is no more than 5mm, and the measurable lesions have not received local treatments such as radiotherapy or cryotherapy);

Inclusion Criteria

- (6) ECOG PS: 0-2;
- (7) Estimated life expectancy ≥3 months;
- (8) Adequate hematological function, defined as an absolute neutrophil count of ≥1.5×10^9/L, a platelet count of ≥80×10^9/L, and hemoglobin ≥90g/L (without transfusion or correction with G-CSF or other hematopoietic growth factors within 7 days);
- (9) Adequate liver function, defined as a total bilirubin level \leq 1.5 times the upper limit of normal (ULN) and levels of aspartate aminotransferase (AST) and alanine aminotransferase (ALT) \leq 2.5 times ULN for all patients;
- (10) Adequate renal function, defined as a creatinine clearance rate ≥50ml/min (Cockcroft-Gault formula);
- (11) Adequate coagulation function, defined as an international normalized ratio (INR) or prothrombin time (PT) ≤1.5 times ULN; if the subject is receiving anticoagulant therapy, as long as the INR/PT is within the range specified for the anticoagulant medication, it is acceptable;

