influenza are permitted; however, live attenuated influenza vaccines administered nasally are not allowed; (19) Have a medical history, disease, treatment, or laboratory abnormalities that may interfere with the trial results, prevent full participation in the study, or that the investigator deems participation in the study is not in the best interest of the subject; (20) Have local or systemic diseases caused by non-malignant tumors, or secondary reactions to cancer that could lead to increased medical risks and/or uncertainty in the evaluation of life expectancy. (21) The investigator deems the subject unsuitable for inclusion. 1. Sintilimab: 100 mg/10 ml, 200 mg, administered via intravenous infusion on Day 1, Q3W (every 3 weeks) 2. Carboplatin: AUC 5 mg/ml/min, administered via intravenous infusion on Day 1, Q3W Study 3. Cisplatin: 20 mg/vial, 75 mg/m^2, administered via intravenous Medication infusion on Day 1, Q3W and Administration 4. Etoposide: 100 mg/5 ml, 100 mg/m², administered via intravenous Method infusion on Days 1-3, Q3W Continue until disease progression, death, intolerable toxicity, withdrawal of informed consent, initiation of new antitumor treatment, or termination for other reasons specified in the protocol, with a maximum duration of Sintilimab use of 2 years. Therapeutic Efficacy Assessment: - The investigator will assess therapeutic efficacy according to RECIST 1.1. The evaluation includes progression-free survival (PFS), 1-year PFS rate, overall survival (OS), and objective response rate (ORR). Safety Assessment: **Evaluation** - The incidence, relationship to the study medication, and severity of Criteria all adverse events (AEs), treatment-related adverse events (TRAEs), immune-related adverse events (irAEs), and serious adverse events (SAEs); - The number of subjects who discontinue the study due to the aforementioned adverse events: - Changes in vital signs, physical examination results, and laboratory results before, during, and after the study treatment.

The statistical analysis primarily employs programming calculations using the SPSS statistical analysis software. Statistical tests utilize one-tailed and two-tailed tests, with a P-value less than or equal to 0.05 considered to indicate a statistically significant difference, and the confidence interval adopts a 95% confidence level.

Statistical Methods

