4.1 Inclusion Criteria

- (1) Age: ≥18 years and ≤75 years old;
- (2) A diagnosis of extensive-stage small cell lung cancer confirmed by pathology (including histology or cytology);

- (3) Previously untreated patients who have not received any systemic antitumor therapy;
- (4) Asymptomatic patients with brain metastases, or those with brain metastases that have been treated and have maintained a clinically stable condition for at least one month, and have not used steroids and anticonvulsant drugs for at least one month before entering the study:
- (5) Measurable lesions (according to RECIST 1.1 criteria, the longest diameter of the tumor lesion on CT scan is ≥10mm, the shortest diameter of the lymph node lesion on CT scan is ≥15mm, the scan slice thickness is no more than 5mm, and the measurable lesions have not received local treatments such as radiotherapy or cryotherapy);
- (6) ECOG PS: 0-2 points;
- (7) Expected survival of ≥3 months;
- (8) Adequate hematological function, defined as an absolute neutrophil count of ≥1.5×10^9/L, platelet count of ≥80×10^9/L, and hemoglobin ≥90g/L (no blood transfusion history within 7 days, and not corrected with G-CSF or other hematopoietic growth factors);
- (9) Adequate liver function, defined as a total bilirubin level ≤1.5 times the upper limit of normal (ULN) and aspartate aminotransferase (AST) and alanine aminotransferase (ALT) levels ≤2.5 times ULN for all patients;
- (10) Adequate renal function, defined as a creatinine clearance rate ≥50ml/min (Cockcroft-Gault formula):
- (11) Adequate coagulation function, defined as an international normalized ratio (INR) or prothrombin time (PT) ≤1.5 times ULN; if the subject is undergoing anticoagulant therapy, as long as INR/PT is within the range specified for the anticoagulant medication;
- (12) For female subjects of childbearing age, a negative urine or serum pregnancy test should be presented within 3 days before the first administration of the study drug. If the urine pregnancy test result cannot be confirmed as negative, a blood pregnancy test is required:
- (13) If there is a risk of conception, male and female patients must use effective contraception (i.e., a method with a failure rate of less than 1% per year) and continue to do so for at least 180 days after stopping the trial treatment; Note: If abstinence is the subject's usual lifestyle and the preferred method of contraception, then abstinence can be accepted as a contraceptive method;

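### The blood-product example in Section 8.4.4 conflicts with the SAE definition and lets a transfusion-only admission for on-study cytopenia lose SAE status

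*Protocol*

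**What the plan says.** Four parts of the protocol bear on this.

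- **Definition of an SAE.** Section 8.4 includes "Events that require hospitalization or prolongation of hospital stay" as a seriousness criterion and makes no exception for transfusion. Section 8.4.4 opens the same way: "Adverse events that result in hospitalization or prolongation of hospital stay during clinical research should be considered serious adverse events". It sets no minimum stay: "Any initial admission to a medical institution (even if less than 24 hours) meets this criterion".
- **Exemption list.** Later in 8.4.4 the lead-in reads "Hospitalization or prolongation of hospital stay not related to the worsening of adverse events (AEs) itself is not a serious adverse event (SAE"), and examples follow. The last is "Hospitalization solely due to the use of blood products".
- **Entry counts.** Inclusion criterion 8 requires platelets of at least 80×10^9/L and haemoglobin of at least 90 g/L. The synopsis words the haemoglobin part as "hemoglobin ≥90g/L (without transfusion or correction with G-CSF or other hematopoietic growth factors within 7 days"), and Section 4.1 adds "no blood transfusion history within 7 days, and not corrected with G-CSF or other hematopoietic growth factors".
- **Use of the SAE classification.** The synopsis, under Evaluation Criteria, lists the incidence, relationship and severity of AEs, treatment-related AEs, "immune-related adverse events (irAEs), and serious adverse events (SAEs"). Section 8.5 requires SAEs to reach the sponsor within 24 hours, with onward reporting to the regulator and ethics committee.

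**The concern.** The blood-product example gives an investigator a reason to classify as non-serious an admission that the rest of the section classifies as serious. In a platinum-etoposide trial, an admission to transfuse for anaemia or thrombocytopenia is a foreseeable event, not a remote one. Two investigators could classify the same admission in opposite ways and each cite Section 8.4.4.

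The SAE count and the expedited report are at stake. The effect has one direction, because the example can only take events out of the SAE category. The trial has a single arm, so there is no comparator in which the same under-classification would occur and offset it.

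**Working it through.** The protocol states no figure that can be reproduced here, so the check sets the provisions side by side.

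**1. One admission, three provisions.** Take a patient whose haemoglobin falls during chemotherapy and who is admitted for red cells, with no other reason for admission.

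| Provision | Classification |
|---|---|
| Section 8.4, hospitalisation criterion | SAE |
| Section 8.4.4, opening rule | SAE: the anaemia is an AE and it led to admission |
| Section 8.4.4, blood-product example | Not an SAE |

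**2. Is the example limited by its own wording?** The other examples of admissions in the list carry a limit. They cover a pre-existing condition with no new or worsened event, an administrative reason, a stay that the protocol requires, or an elective stay unrelated to worsening events. The blood-product example is limited only by the word for exclusivity of purpose. It says nothing about why blood products were needed.

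**3. Will the need for blood products usually be an adverse event in this trial?**
- Entry requires haemoglobin of at least 90 g/L and platelets of at least 80×10^9/L, untransfused for 7 days (inclusion criterion 8).
- Treatment is carboplatin or cisplatin plus etoposide for 4 or 6 cycles (Section 5.1).
- Table 7 provides for platelets below 50×10^9/L, with or without bleeding. From the entry minimum, that is a fall of more than 80 − 50 = 30×10^9/L. Table 7 governs dose adjustment and does not mention admission or transfusion. It shows only that cytopenia is expected.
- Section 8.4.5, under pre-existing conditions, makes a sign present at screening an AE if it increases in severity, frequency or nature.

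An admission only to transfuse will therefore usually follow a new or worsened cytopenia, which is an AE. This is an inference from the entry criteria, because the protocol gives no transfusion threshold or rate.

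**4. What remains if the example applies?** The paragraph on procedures in 8.4.4 still has the condition behind a procedure reported, but its appendicitis illustration is at AE level. That keeps the cytopenia in the AE tables and does not restore its seriousness. The SAE classification and the Section 8.5 report are what is lost.

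**5. Size.** Let k be the number of patients whose only SAE is a transfusion-only admission, with the planned 45 patients as denominator. Patient-level SAE incidence is understated by k/45. The values of k below are assumptions that show the scale; they are not estimates.

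| k | k/45 | Understatement (percentage points) |
|---|---|---|
| 0 | 0/45 | 0 |
| 1 | 1/45 | 2.2 |
| 3 | 3/45 | 6.7 |
| 5 | 5/45 | 11.1 |

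**The case against.** The best defence is the lead-in. It restricts the whole list to admissions unrelated to worsening adverse events. Read with the opening rule and the pre-existing-conditions paragraph, it would leave an admission for new or worsened cytopenia outside the list and still an SAE. That reading is available, but it does not remove the conflict. The blood-product admission is offered as an instance of the exempt class, so it tells the investigator that such an admission is unrelated to worsening. If the lead-in overrides it, the example has little left to cover in patients who enter with these counts.

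Several narrower objections stand and limit the point:

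- The exemption reaches only admissions solely for blood products. An admission that also has another cause, such as bleeding or febrile neutropenia, stays an SAE. So does any event that is fatal or life-threatening under Section 8.4.
- The cytopenia is still recorded, graded by CTCAE 5.0 and tabulated, and the laboratory summaries in Section 9.2 cover it.
- Haemoglobin of 90 g/L or platelets of 80×10^9/L can already be low, and the untransfused window is 7 days. Some on-study transfusions could therefore reflect an unworsened baseline condition, which the list may properly exempt.
- The secondary safety endpoint is the incidence of AEs. SAE incidence is a descriptive evaluation named in the synopsis, and no numerical decision rule uses it. The lead-in period counts dose-limiting toxicities, and the early-termination criterion in Section 4.4.3 refers to adverse drug reactions.

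A reader might infer that all hospitalised haematological toxicity drops out of the SAE count, or that the SAE rate will be several points too low. The documents support neither. The first ignores the exclusivity wording and the other seriousness criteria. The second needs a rate of transfusion-only admissions that the protocol does not give, and the true effect could be zero.

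**Conclusion.** The point holds within a limited scope. The blood-product example contradicts the SAE definition in Section 8.4, the opening rule of 8.4.4 and the lead-in to its own list. It allows a transfusion-only admission for an on-study cytopenia, meeting no other seriousness criterion, to lose SAE status and 24-hour reporting. Any effect on the SAE incidence named in the synopsis is downward.

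The textual conflict is certain and its numerical effect is unknown. Each affected patient with no other SAE lowers incidence by 2.2 percentage points, taking 45 patients as the denominator. That most such admissions would reflect a new or worsened cytopenia rests on the entry counts and the chemotherapy backbone, not on observed data. The correction should be made because it is cheap and affects a named safety evaluation. It has no bearing on the primary endpoint or the sample size.

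**What to change.** Reconcile Sections 8.4 and 8.4.4. Limit the blood-product example to admission for a condition that was present before the first dose and has not worsened. Add a sentence stating that admission or prolonged stay to transfuse a new or worsened cytopenia is an SAE, reported under the diagnosis that made the transfusion necessary. This fits the existing instruction in 8.4.4 to use the diagnosis as the reporting term when an SAE leads to death.

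The cost is a sentence or two of protocol text, a few more SAE forms and possibly a slightly less favourable SAE rate. Only event classification and reporting change; transfusion practice, dosing and other patient management are untouched.
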